The entire pilot study phase for this project will be completed over the course of six months. We plan to enroll 30 adolescents, aged 16-19 to playtest our game. We will meet with participants between 2-4 times for approximately 1-1.5 hours each time, over the course of two to four weeks. Participants will complete baseline measures, two gameplay sessions and a post-assessment to measure feasibility, acceptability, and usability. Each participant will complete the pilot study within two to four weeks. We will meet with them after school in a classroom (securing room with coordination from our school partners). When the study is introduced to parents/guardians and students, we have always stressed that a stipulation of our studies requires reliable transportation to/from our studies. In certain cases, we will provide a bus pass.

All participants will be assigned a study identification number to link pre/post assessments and to conduct focus groups. Data collection and storage will be conducted according to standardized protocols. The link between participant's identity and the study number is confidential and will be kept separate from all study data. Research data, such as informed consents/assents, transcriptions, and field notes, is kept in cabinets that are locked except when in use, and access to

data stored in computers is password protected. We will collect participants' names, school, gender, grade level, age, race, and ethnicity. Names will not be sent to any third parties. Any data shared with NIH or other third-party organizations will be aggregate data. We will collect this information and it will be stored in a secured database.

The Yale University Human Subjects Committee (the committee that reviews, approves, and monitors research on human subjects) may inspect study records. All published results will be group data. Information that will be collected during the focus group interviews will be erased 12 months after the completion of the study and after review of their content has been completed.

1. Formative and development work: (1 year)

- a.) We will work iteratively with our target audience of 16-19-year old adolescents within schools to develop videogame content, collecting qualitative data for the videogame intervention and refining our logic model with input from 8 focus groups of 5 adolescents each (n=40), aged 16-19 and 4 focus groups of 5 young adults aged 18-25 (n=20).

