- a.) We will work iteratively to develop videogame content, conducting 8 focus groups of 5 adolescents each (n=40), aged 16-19 and 4 focus groups of 5 young adults each (n=20), aged 18-25 collecting qualitative data for the videogame intervention and to refine our logic model.
- b.) Working with our community school partners, we will engage 1-2 schools and school-

based health centers to **recruit** 30 adolescents for our subsequent pilot study. Given participants are only involved in the pilot study for several weeks and given our track record of having retained the majority of participants for over two years of a prior RCT, we are not concerned about retention.

- c.) We will **pilot-test** the intervention with 30 adolescents, aged 16-19, in conjunction with their schools, to evaluate the **acceptability** of the game. To garner feedback, we will collect data (both qualitative and quantitative) after the completion of game play sessions. The pilot will either be conducted virtually or in person. For the in person segment of the pilot, all COVID-19 protocols and procedures that are in place at our partner school site will be followed.
- d.) We will also **pilot procedures** such as assuring the gameplay sessions go smoothly and that data collection is streamlined in anticipation of conducting the subsequent RCT.
- e.) We will develop a game implementation manual that will be used during the subsequent RCT, as needed, by school and school-based health center staff.
- f.) As part of our focus groups with school-based health affiliates, we will collect focus group data for our formative and development of a videogame intervention from the Youth Advisory Council (n=15) and School-based health affiliates (n=25) at the annual School-Based Health Alliance Convention. This includes data on implementation strategies such as barriers and facilitators and to share perceptions of the newly created game and provide input on the game implementation manual. This will take place at the annual School-Based Health Alliance Convention with our national partners who will help recruit participants for the Youth Advisory Council and School-Based Health Alliance.

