- c. Include an appropriate Data and Safety Monitoring Plan. Examples of DSMPs are available here <http://your.yale.edu/policies-procedures/forms/420-fr-01-data-and-safety-monitoring-plans-templates> for
 - i. Minimal risk
 - ii. Greater than minimal

[name] will not be involved with any participant recruitment and/or data management nor data analysis. [name] is appointed as the co-investigator who will be independent of [name] review over subject selection and adverse event reporting responsibilities.

We are in the process of establishing a Data and Safety Monitoring Board (DSMB) that will also be in place for the subsequent randomized controlled trial. The DSMB will be comprised of two experts in clinical trials in adolescents (one with expertise in substance use prevention) and an expert in statistical analysis of clinical trials and will provide oversight in a number of areas including for the selection, enrollment, or consenting of participants, or determination of eligibility.

- d. For multi-site studies for which the Yale PI serves as the lead investigator:
 - i. How will adverse events and unanticipated problems involving risks to subjects or others be reported, reviewed and managed? *Write here*
 - ii. What provisions are in place for management of interim results? *Write here*
 - iii. What will the multi-site process be for protocol modifications? *Write here*

12. Statistical Considerations: Describe the statistical analyses that support the study design.

Data analyses general considerations: Statistical procedures and models for analyzing data have been selected according to the research hypotheses and the types of data available. In general, we will use two-tailed tests and p-values smaller than 0.05 will be considered statistically significant. When necessary, we will adjust the level of significance (alpha) to account for multiple statistical tests. All statistical analyses will be conducted on an intention-to-treat sample using either SPSS or SAS statistical packages.

SECTION II: RESEARCH INVOLVING DRUGS, BIOLOGICS, RADIOTRACERS, PLACEBOS AND DEVICES

If this section (or one of its parts, A or B) is not applicable, check off N/A and delete the rest of the section.

A. RADIOTRACERS **N**

B. DRUGS/BIOLOGICS **N**

B. DEVICES

c::::::J c::::::J c::::::J c::::::J SECTIONIII: RECRUITMENT/CONSENTAND ASSENTPROCEDURES

1. Targeted Enrollment: Give the number of subjects:

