If appropriate, has a Certificate of Confidentiality been obtained? Following newguidelines enacted in 2017, the NIDA/NIH will automatically grant a COC for this project.

SECTION V: POTENTIAL BENEFITS

Potential Benefits: Identify any benefits that may be reasonably expected to result from the research, either to the subject(s) or to society at large. (Payment of subjects is not considered a benefit in this context of the risk benefit assessment.)

It is anticipated that the young adolescents enrolled in this study should benefit directly from the study as the purpose of the study is to improve their attitudes, intentions, and knowledge, and decision-making around health promotion and opioid use. This research has the potential to benefit a large number of youth around the country and worldwide, because if in the pilot test the intervention is shown to be effective, then this intervention can be replicated elsewhere and with a greater ease of dissemination. The potential benefits to participants are great and strict precautions are being taken to protect the confidentiality and well-being of participants, as has been described above. Thus, the potential benefits to the participants outweigh the potential risks.

SECTION VI: RESEARCH ALTERNATIVES AND ECONOMIC CONSIDERATIONS

1. **Alternatives:** What other alternatives are available to the study subjects outside of the research?

No participation in the study

2. **Payments for Participation (Economic Considerations):** Describe any payments that will be made to subjects, the amount and schedule of payments, and the conditions for receiving this compensation.

Each participant (adolescents and young adults) will receive a \$30 gift card for participating in the game development focus group.

Each participant will receive a \$30 gift card for participating in the individual interviews conducted with adolescents and young adults who are currently in treatment for opioid use disorder.

Each participant will receive a \$30 gift card for participating in the individual interviews conducted with treatment providers who have treated individuals 16-35 for opioid use disorder in the last 5 years.

Participants in the pilot study will either receive a \$25 gift card for one two-hour gameplay session and follow-up questions (in person) OR two gift cards totaling \$60 for six one hour gameplay sessions and follow-up questions (virtually).

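### Acceptability and usability are rated in one post-assessment after gameplay, with nothing described for a participant who stops early, so the intention-to-treat analysis may lack ratings from those likeliest to dislike the game

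*Combined protocol and SAP*

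**What the plan says.** The pilot description in item 4 (Research Plan) gives the size, "We plan to enroll 30 adolescents, aged 16-19 to playtest our game", and then the sequence: "Participants will complete baseline measures, two gameplay sessions and a post-assessment to measure feasibility, acceptability, and usability". It also says that a study number will link assessments made before and after play. Item 2(c) of the same plan, on pilot feasibility and acceptability work, repeats the timing of the feedback: "we will collect data (both qualitative and quantitative) after the completion of game play sessions".

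On attrition, item 2(b) says "we are not concerned about retention". It gives two reasons: involvement lasts only weeks, and an earlier randomised trial kept most of its participants for more than two years. No dropout allowance is stated.

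Item 12 (Statistical Considerations) says "All statistical analyses will be conducted on an intention-to-treat sample". It does not define that sample for a single-group pilot, and it does not say how a participant without a post-assessment is handled. The data-management text in Section IV provides completeness checks and queries, but no analysis rule.

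Two other places bear on exposure. Subject Population (item 6) splits the pilot into 2 virtual groups of 3 and 6 in-person groups of 4. Payments for Participation (Section VI, item 2) describes a single two-hour session for in-person participants and six one-hour sessions for virtual participants, with follow-up questions in both cases. The Research Plan describes two sessions for everyone.

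**The concern.** Acceptability is the declared purpose of the pilot test, and the pilot prepares a subsequent randomised trial. A game that players abandon has failed on acceptability, yet the plan describes no way of obtaining a rating from someone who abandons it. If such participants have no rating, the figure reported is that of the participants who stayed, whatever the analysis set is called. Because the reason for leaving is plausibly tied to the rating itself, the missing ratings would not be a random subset, and the error would tend to favour the game. This is a data-collection gap: an analyst cannot recover a rating after the pilot has closed.

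**Working it through.** **Inputs from the documents.** Pilot size 30 (Research Plan). Groups: 2 × 3 = 6 virtual and 6 × 4 = 24 in person (Subject Population). The sum 6 + 24 = 30 reproduces the stated size. There is nothing else to reproduce, because the plan gives no acceptability threshold, expected rate, precision, power or dropout figure for the pilot.

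**Step 1: is the assessment after each session or at the end?** Read alone, item 2(c) could mean after each session. The pilot description lists one post-assessment, after two gameplay sessions, and names it as the measure of all three outcomes. Taken together, a single end-of-play assessment is the natural reading.

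**Step 2: what is undetermined.** Let q of the 30 have no rating and let x of the 30 − q rated participants find the game acceptable.
- Completer-only proportion: x/(30 − q).
- All-enrolled proportion: at least x/30 (unrated counted as not acceptable) and at most (x + q)/30 (unrated counted as acceptable).
- Width of that range: q/30, whatever x is.

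So q = 1 gives 3.3 points, q = 3 gives 10 points, q = 6 gives 20 points, and q = 0 gives none.

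**Step 3: illustration.** *Assumption:* about 80% of rated participants find the game acceptable.

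| q | Completers only | All 30, lower bound | All 30, upper bound | Completers minus lower bound |
|---|---|---|---|---|
| 0 | 24/30 = 80.0% | 24/30 = 80.0% | 24/30 = 80.0% | 0 |
| 1 | 23/29 = 79.3% | 23/30 = 76.7% | 24/30 = 80.0% | 2.6 points |
| 3 | 22/27 = 81.5% | 22/30 = 73.3% | 25/30 = 83.3% | 8.1 points |
| 6 | 19/24 = 79.2% | 19/30 = 63.3% | 25/30 = 83.3% | 15.8 points |

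**Step 4: the adverse case.** *Assumption:* 24 of 30 would find the game acceptable (80%, exact 95% interval 61.4% to 92.3%) and every leaver comes from the other six. The completer-only figure is then:
- one leaver: 24/29 = 82.8% (+2.8 points)
- two leavers: 24/28 = 85.7% (+5.7 points)
- three leavers: 24/27 = 88.9% (+8.9 points)
- six leavers: 24/24 = 100% (+20 points)

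**Step 5: who could leave between sessions.** With two sessions for everyone (Research Plan), all 30 could. With the schedule in the payments section, only the 6 virtual participants have a later session to miss, so leaving between sessions could make at most 6/30 = 20 points undetermined. Stopping within a session is possible for anyone under either schedule.

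**The case against.** Several points on the other side have force.

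*Stopping is not invisible.* Section IV describes automatic logging of game state and player decisions in every session, so anyone who logs in and then stops leaves a record. A reader might infer that feasibility too is observed only at the end, or that stopping is hidden; the logs show otherwise. What remains is that the logs record progress and choices, not opinions of the game, and that the plan does not name them as outcomes.

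*Exclusion is not stated.* A reader might infer a completer-only design. No text says that a participant who stops is refused the post-assessment, and the plan lists that assessment separately from the gameplay sessions. The documents are silent, so this is an unaddressed risk.

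*Exposure is short.* The plan's first reason for not worrying about retention is that involvement lasts only weeks, which is fair. A reader might also take the retention of most participants in the earlier trial to mean barely more than half. That phrase describes more than two years in a different study and does not support a dropout figure here. On the payments schedule, 24 of 30 have one session with questions following it, which leaves little room to leave before being asked.

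*Rating after use is ordinary.* Assessing usability once play is finished is normal in a short playtest. That stands. The gap is only the absence of a provision for those who do not finish.

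**Conclusion.** The point holds as a gap in data collection and in the definition of the analysis set, and it should be closed before the pilot enrols. The plan describes one post-assessment after gameplay, no assessment on stopping, and an intention-to-treat label that cannot supply uncollected ratings. The likely direction is upward, on the assumption that those who stop tend to like the game less.

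The size cannot be fixed from the documents. It is zero if nobody stops; otherwise q/30 of the acceptability proportion is undetermined. A reader might take a bias of 9 to 20 points as established. That range requires three to six leavers, every one of whom would have rated the game unacceptable; one or two such leavers give 2.8 or 5.7 points, and the documents supply neither a dropout rate nor an acceptability rate. How many participants are exposed to the risk between sessions, all 30 or mainly the 6 virtual ones, depends on which session schedule applies, and the documents conflict on this.

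**What to change.** - **Collect on stopping.** Give anyone who stops the short acceptability and usability items and one question on the reason, at the point of stopping. For participants with more than one session, give the items at the end of each session. The measures are still to be finalised and loaded into REDCap, so this can be built in.
- **Define the set.** Replace the intention-to-treat wording with all enrolled participants.
- **Report bounds.** State in advance what rating counts as acceptable. Report acceptability over all 30, once with unrated participants counted as not acceptable and once as acceptable, with the completer-only figure as secondary. The bounds cover anyone who declines the exit items.
- **Do not carry the last rating forward as the main rule.** That rating was given before the participant decided to stop and can keep the same upward bias.
- **Use what is already recorded.** Name session attendance and logged game progress as feasibility outcomes.
- **Reconcile the schedules.** The Research Plan and the payments section must agree on the number of sessions for each mode.

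The cost is a few minutes per session, some added burden from repeated items, one additional form and a wording change. The reported acceptability may look less favourable.

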Most opioid misuse begins during adolescence and young adulthood. Adolescence is the time to intervene with prevention interventions (i.e., interventions focused on adolescents who have not yet misused opioids) in settings like school-based health centers (HCs), yet few interventions exist that prevent initiation of opioid misuse. “Serious videogame” interventions can improve health behaviors. They meet adolescents “where they are,” and compared to standard interventions, they can reach large populations, with consistent fidelity, place limited demands on personnel/resources, and facilitate rapid sustainable distribution, all at a potentially lower cost. This study harnesses the power of videogame interventions and incorporates components of effective substance use prevention programs to develop an evidence-informed intervention to prevent the initiation of opioid misuse in adolescents. Building on our experience developing videogame interventions and in partnership with the national School-Based Health Alliance (SBHA), we will develop and test a new videogame intervention, *PlaySmart*. *PlaySmart* will build upon our *PlayForward* videogame intervention platform that has demonstrated efficacy in improving attitudes and knowledge related to risk behaviors. Through rigorous formative work and with input from adolescents, and our SBHA and game development partners, we will create the *PlaySmart* videogame intervention. *PlaySmart* will be designed to provide players with behavioral skills and knowledge through repetitive and engaging videogame play to target adolescent perception of risk of harm from initiating opioid misuse. The specific aims of this proposal are to: 1) develop the *PlaySmart* game and implementation strategies through focus groups as part of our formative work; and 2) pilot-test the *PlaySmart* game. We will be working with local schools as well as SBHA stakeholders and partners. The gap in the research on preventing initiation of opioid misuse in youth and in implementing prevention programs with good fidelity needs to be urgently addressed given the high prevalence of adolescent opioid misuse and overdose. This research has the potential to create a videogame intervention to prevent initiation of opioid misuse with far-reaching and sustained impact on adolescents.

2. Probable Duration of Project: State the expected duration of the project, including all follow-up and data analysis activities.

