- b.) We will aim to conduct up to 20 individual interviews with participants who are aged 16-25 and who are currently receiving treatment for opioid use disorder to learn about their stories and experiences to develop videogame content, collect qualitative data for the videogame intervention, and refine our logic model with input from participants.
- c.) We will aim to conduct up to 20 individual interviews with treatment providers of opioid use disorder that have provided medical services for individuals aged 16-35 within the last 5 years to learn about their stories, experiences and perspectives to develop videogame content, collect qualitative data for the videogame intervention, and refine our logic model with input from participants.
- d.) We will aim to conduct focus groups of 5-6 individuals of up to 20 stakeholders (educators, prevention specialists etc.) aged 19-80 to learn about their experiences and recommendations to develop videogame content and refine our logic model.
- e.) We will create the "Game Playbook" specific to this new **PlaySmart** intervention. Game Playbooks are our intervention manuals. We create behavior change gameplay manuals to accommodate the specific needs of a multi-disciplinary game development team. The playbooks outline the theoretical foundations and gameplay elements. This ensures targeted theoretical principles and behavior change mechanisms are included in the videogame intervention.
- f.) We will adapt and refine the current **PlayForward Platform** to develop the new **PlaySmart** game intervention by creating new content, developed from focus groups and from the substance use prevention literature, for our game development team, Schell Games, to adapt the current platform to develop the new **PlaySmart** game.
- g.) While developing the game content, we will simultaneously be finalizing our assessment measures. This strategy ensures that what we are testing is in the content of the game and that the game provides the information and skill-building that our measures will assess. Once we have finalized our assessment measures, we will have them loaded into REDCap, the Web-based computer system that will be managed by our collaborators at the Yale Center for Analytical Sciences (YCAS), and this system will be used for data collection, management, and monitoring.

2. Pilot feasibility and acceptability work: (1 year)

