For interviews with treatment providers of opioid use disorder, up to 20 adults (19-80) who have treated individuals aged 16-35 for opioid use disorder within the last 5 years will be recruited. Clinical directors at each APT Foundation location will inform treatment providers about our study and other colleagues may be contacted via email and from snowball sampling from other providers that participate in the interviews. Interested participants will contact our research team to participate.

For focus groups with stakeholders (educators, prevention specialists, etc.), approximately 20 adults (19-80) will be recruited. Our team may collaborate with various organizations (e.g., FCD Prevention Works, First Book) to recruit participants. Interested participants will contact our research team to participate.

Subject classification: Check off all classifications of subjects that will be specifically recruited for enrollment in the research project. Will subjects who may require additional safeguards or other considerations been enrolled in the study? If so, identify the population of subjects requiring special safeguards and provide a justification for their involvement.

181 Children	181 Healthy	 Fetal material, placenta, or dead fetus
 Non-English Speaking	 Prisoners	 Economically disadvantaged persons
 Decisionally Impaired	 Employees	 Pregnant women and/or fetuses
 Yale Students	 Females of childbearing potential	

NOTE: Is this research proposal designed to enroll children who are wards of the state as potential subjects?

Yes **No**

7. Inclusion/Exclusion Criteria: What are the criteria used to determine subject inclusion or exclusion?

Adolescent participants must: 1) attend high school that has a school-based health center, and 2) be 16-19 years (grades 9-12) to participate in the game development focus groups or pilot testing OR they must be a member of the School-Based Health Association Youth Advisory Council to solely participate in the focus groups.

Young adult game development focus group participants must be 18-25 years old.

Adult participants that will be participating in focus groups during the game development phase must be national school-based health center personnel and be between the ages of 19-80.

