Interviews with individuals in treatment: Participants must be between the ages of 16-25, receiving treatment for an opioid use disorder, a device to access the internet for the virtual interview and be able to sit for 60-90 minutes in an interview.

Treatment providers: Participants must be adults between the ages of 19-80, have provided medical treatment for individuals aged 16-35 in the last 5 years for opioid use disorder, a device to access to the internet for the virtual interview, and be able to sit for 60-90 minutes for an interview.

Stakeholders: Participants must be between the ages of 19-80, qualify as a stakeholder in the project (e.g., an educator, prevention specialist, etc.), have access to a device to access the internet for a virtual focus group, and be able to sit for 60-90 minute for a focus group.

8. How will eligibility be determined, and by whom? Write here

For youth focus groups & pilot study: In order to be eligible for either the youth focus groups or the pilot study, adolescent participants must: 1) attend a high school that has a school-based health center, 2) be 16-19 years (grades 9-12), and 3) coordinate reliable transportation home or to their next location. The research assistant (in collaboration with the designated school liaison/champion) will screen for eligibility and discuss the study with the participant and their parent/guardian.

For young adult focus group participants: In order to be eligible for the young adult focus group the participant must be between the ages of 18-25.

For adult focus groups: In order to be eligible for the adult focus group, the participant must be a school-based health center affiliate and between the ages of 19-80.

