Participation in this study will be strictly voluntary, confidential, and non-discriminatory. Participants will be enrolled either on-site or virtually during their first meeting. The study team will enroll adolescents, aged 16-19 years (grades 9-12) from schools with school-based health centers. In partnership with school-based health centers, we will provide flyers and announcements to the general population of students via school meetings and physical education/health classes. In collaboration with community program staff, we will discuss the study with interested adolescents and parents/guardians (for those participants ages 16-17) and collect eligibility screening data. In describing the study to the participant, the purpose of the study will be described as "finding out how kids can make choices and decisions that are healthier for them." It is important to note that this part of the study is NOT about engaging youth who already misuse opioids; the focus of this part of study is on prevention. In describing the study to the parent/guardian, we will indicate that the study will focus on promoting healthy behaviors in adolescents, and on providing strategies to assist adolescents in making decisions about the many challenges they face during adolescence, including the risks associated with drug misuse. If the participant is eligible and interested, we will proceed with the consent procedures. On separate occasions, we will give information sheets to the adolescents and to their parents describing the purpose of and protocol for the focus groups and pilot-testing depending on the stage of study. For participants under age 18, parents/guardians who do not wish for their teens to participate may contact the research staff for clarification on purpose and/or protocol. As we have done with all of our other HIC protocol, we will provide all of our focus group participants an information sheet and they may opt-out of them. No forms will be signed for focus group participation. Consent and assent documents will be signed for pilot study participation.

9. **Risks:** Describe the reasonably foreseeable risks, including risks to subject privacy, discomforts, or inconveniences associated with subjects participating in the research.

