If there are concerns about issues raised with regards to substance use or mental health, or if participants need additional or more intensive attention, the research staff will contact [name] or [name] (who is a Licensed Professional Counselor and has extensive expertise working with adolescents and schools) who will discuss providing further consultation to the participant.

It is anticipated that the adolescents enrolled in this study should benefit directly from the study as the purpose of the study is to facilitate increasing their perception of risk of harm from initiating the misuse of opioids, decreasing their actual misuse of opioids, as well as improving their decision making and knowledge to optimize their abilities to negotiate around risky behaviors. The potential benefits to participants are great while strict precautions are being taken to protect the confidentiality and well-being of participants, as has been described above. Thus, the potential benefits to the participants outweigh the potential risks.

10. **Minimizing Risks:** Describe the manner in which the above-mentioned risks will be minimized.

This study presents minimal risks to the participants and adverse events or other problems are not anticipated.

Adverse Events (AEs):

Violation of confidentiality: Any breach of confidentiality.

Discomfort due to assessment procedures: Discomfort created by answering survey questions.

Embarrassment in disclosing sensitive personal information.

Disclosure of information about current and/or intended physical harm to persons; current and/or intended abuse of children that would be reported to a child welfare agency; and/or an investigation of such allegation(s) that could ensue.

Dissatisfaction with the intervention activities: In this case it would be the game intervention.

While gaming addiction is a recognized entity, it is very rare and, in the setting of playing a serious game, very unlikely. If there are any concerns of developing serious addictive behaviors in our pilot study participants, we have team members who are experts in the field of addiction medicine and will address these issues immediately.

Serious Adverse Events (SAEs):

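### Does the pilot need a rule for prior opioid misuse, given that the game is meant for adolescents who have never misused?

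*Combined protocol and SAP*

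**What the plan says.** The opening summary of the protocol explains prevention interventions as "interventions focused on adolescents who have not yet misused opioids" and presents PlaySmart as one of them. Section I, item 8 (eligibility) adds that "this part of the study is NOT about engaging youth who already misuse opioids".

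The entry rules do not carry this through. Item 7 (Inclusion/Exclusion Criteria) reads "Adolescent participants must: 1) attend high school that has a school-based health center, and 2) be 16-19 years (grades 9-12". Item 8 repeats this and adds transport: "2) be 16-19 years (grades 9-12), and 3) coordinate reliable transportation home or to their next location". Neither mentions opioid history. Item 8 refers to screening data without listing their content.

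Item 12 (Statistical Considerations) states: "All statistical analyses will be conducted on an intention-to-treat sample using either SPSS or SAS statistical packages". It gives no rule for prior misuse. Item 9 (Risks) counts "decreasing their actual misuse of opioids" among the aims for enrolled adolescents.

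On measurement, item 4 (Research Plan) says: "All participants will be assigned a study identification number to link pre/post assessments". It names feasibility, acceptability and usability as what the pilot assesses in 30 adolescents. Item 4, part 1g leaves the instruments to be finalised alongside the game, so that "the game provides the information and skill-building that our measures will assess". Item 9 notes that some assessment questions deal with drug use.

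**The concern.** A study of preventing a first event would normally either exclude people who have already had the event or say how they will be analysed. This plan does neither. It describes a never-misusing audience in two places, recruits from the student body at large, and elsewhere speaks of reducing misuse that is already present, which cannot apply to someone who has never misused.

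If changes in perceived harm, intentions, self-efficacy or knowledge were reported from the linked assessments, a reader could not tell whether they described the adolescents the game is for. Acceptability carries the same ambiguity to a lesser degree. The pilot also rehearses procedures for a later randomised trial, so an unsettled target population could be carried forward.

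**Working it through.** **Inputs.** From the documents: 30 pilot participants (item 6: 2 groups of 3 plus 6 groups of 4, 6 + 24 = 30) and the named outcomes (item 4). The documents give no misuse prevalence and no effect size. Assumed for scale: lifetime misuse p of 1%, 2%, 5% or 10%, and a difference D of 0.5 to 1 SD in mean change between prior misusers and the rest. The plan has no power or precision figure to reproduce.

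**How many prior misusers?** Expected number = 30p. Chance of at least one = 1 − (1 − p)^30.

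| Assumed p | Expected number | Chance of at least one |
|---|---|---|
| 1% | 0.3 | 26% |
| 2% | 0.6 | 45% |
| 5% | 1.5 | 79% |
| 10% | 3.0 | 96% |

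The chance passes one half at p = 1 − 0.5^(1/30) = 2.3%. Below that, enrolling none is more likely than not.

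**How far would a mean move?** With k prior misusers, the pooled mean differs from the never-misuser mean by (k/30) × D.

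- k = 1: 0.5/30 = 0.017 SD to 1/30 = 0.033 SD.
- k = 3: 1.5/30 = 0.050 SD to 3/30 = 0.100 SD.

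The 95% half-width for a mean change, in SD units, is t(0.975, n − 1)/√n. At n = 30 this is 2.045/5.477 = 0.373. The largest shift considered is 0.100/0.373 = 27% of the half-width. With one prior misuser it is at most 0.033/0.373 = 9%.

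**Named outcomes.** Take acceptability as a proportion and assume that the proportion of prior misusers who find the game acceptable differs from the rest by 50 percentage points. The pooled proportion then moves by (1/30) × 50 = 1.7 points for one prior misuser and (3/30) × 50 = 5 points for three. The approximate 95% half-width at a proportion of one half is 1.96 × √(0.25/30) = 0.179, or 18 points.

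**What would a never-misuser primary analysis cost?**

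- Precision: the half-width becomes 0.380, 0.388 or 0.396 at n = 29, 28 or 27, which is 1.9%, 3.8% or 5.9% wider. This is slight.
- Confidentiality: if results for all 30 and for 29 never-misusers appear together, 30 × mean(30) − 29 × mean(29) returns the remaining adolescent's score, apart from rounding. Item 4 limits published results to group data, and the sample comes from one or two schools.
- Validity: membership would rest on self-report, possibly entered with an assistant supervising (Section IV, data entry methods), in a study whose staff must pass on concerns about substance use (item 10). Under-reporting is likely, so the subset would be of uncertain purity.

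**The case for a change.** The best case for a change is that it is cheap and the inconsistency is certain. One baseline item and one sentence on the analysis set would tell readers whom the results describe, without excluding anyone. The plan gives reasons to expect more than usability results: linked pre/post assessments, measures tied to game content, two-sided tests at 0.05, and a benefits section that contemplates the pilot showing an effect. Item 8 states an intention but supplies no rule to carry it out.

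The inconsistency stands. So does the point that the plan never says whether prior misusers may enrol. The rest is weaker. The passages suggesting wider use describe the game's conceptual model, general analysis conventions or anticipated benefits. None names an antecedent measure as a pilot outcome. The effectiveness wording in Section V is a separate matter. A drug-use item may already be in the assessments, so what is shown to be missing is a stated rule, not the data. Item 12 also does not prevent a descriptive breakdown. Finally, item 6 defines the subjects simply as adolescents aged 16 to 19, and open recruitment is a defensible choice for a game intended for delivery in schools.

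**Conclusion.** No change to the plan follows. The framing and the entry rules do not match, and the aim of reducing existing misuse is loosely worded. Even so, the pilot's named conclusions hold if the plan is followed as written.

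Under assumed prevalences of 1% to 10%, between 0.3 and 3 prior misusers are expected among 30. One to three of them, differing by an assumed 0.5 to 1 SD, would move a pooled mean by 0.02 to 0.10 SD, well inside a half-width of 0.37 SD. A higher prevalence or a larger difference would raise these figures. The documents do not exclude that, and they do not indicate it either.

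Making never-misusers the primary set would exchange this small ambiguity for a self-reported subset and a possible disclosure of one adolescent's score. That is at best a debatable trade-off. Analysts who have the drug-use answers can sensibly report how many prior misusers took part and keep all 30 as the main sample.
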